6.4 SAFETY EVALUATIONS

PHYSICAL AND TARGETED PHYSICAL EXAM

A full physical examination will be conducted during Screening and at study discharge/EOS (e.g. Day 393). A targeted physical assessment will be performed at other visits as determined by the Investigator based on subject symptoms.

VITAL SIGNS

Vital signs including temperature, respiration rate, blood pressure and heart rate will be measured at Screening and at visits specified in the Schedule of Events (Tables 3 and 4).

At the COVID-19 assessment and convalescent visits, temperature, respiration rate, heart rate and oxygen saturation should be performed.

HEIGHT AND WEIGHT

Weight and height will be collected at Screening.

SOCIO-BEHAVIORAL ASSESSMENT

A Socio-behavioral Assessment, including self-reported smoking and vaping history, and self-reported history of exposure to second-hand smoke will be obtained at Screening.

LABORATORY EVALUATIONS

INO-4800	COVID19-311
Inovio Pharmaceuticals, Inc.	Clinical Protocol

Blood samples will be collected at visits specified in the Schedule of Events (Tables 3 and 4). A total of approximately mL 245-330mL of blood will be drawn from each subject over the course of the study (inclusive of relevant safety and immunology samples at regular study visits per Tables 3 and 4). If the subject is evaluated at COVID-19 visits, an additional volume of approximately 85-120mL will be collected. Subjects may be asked to return for additional blood draws if collected blood sample is lost or unevaluable for any reason.

Hematology [Complete blood count (CBC) with automated differential]:

White blood cell (WBC) count, red blood cell (RBC) count, hemoglobin, hematocrit and platelet count will be measured at Screening (Phase 2 segment only) and at visits specified in the Schedule of Events (Tables 3 and 4). Hemoglobin A1c will additionally be performed at Screening (Phase 2 segment only).

Serum chemistry:

Electrolytes [Sodium (Na), Potassium (K), Chloride (Cl), Bicarbonate (HCO3), Calcium (Ca), Phosphate (PO4)], glucose, Blood Urea Nitrogen (BUN), Creatinine (Cr), alkaline phosphatase, aspartate aminotransferase (AST), alanine aminotransferase (ALT), LDH, and total bilirubin (TBili) at Screening (Phase 2 segment only) and at visits specified in the Schedule of Events (Tables 3 and 4).

Urinalysis:

Urine samples will be tested by dipstick for glucose, protein, and hematuria at Screening (Phase 2 segment only) and at visits specified in the Schedule of Events (Tables 3 and 4). If abnormal (presence of protein, hematuria, or glucose \geq 1+), a microscopic examination should be performed.

Serology:

HIV antibody or rapid test will be measured at Day 0 only.

Antibodies to SARS-CoV-2 will be measured at Screening and at visits specified in the Schedule of Events (Tables 3 and 4).

Pregnancy Testing:

Pregnancy testing will be performed on women of childbearing potential (WOCBP). All women will be assumed to be of childbearing potential unless they are:

- Women who are post-menopausal as defined by reported spontaneous amenorrhea for ≥ 12 months;
- Women who are surgically sterile or have a partner who is sterile (i.e., vasectomy in males or tubal ligation, absence of ovaries and/or uterus in females). In the case of a vasectomy, subjects should wait six (6) months post-vasectomy to be considered sterile.

Phase 2: For WOCBP, a serum pregnancy test will be obtained at Screening and a urine pregnancy test will be performed immediately prior to any dosing and at the subject's last visit.

Phase 3: For WOCBP, a urine pregnancy test will be obtained at Screening and will be performed immediately prior to any dosing.

A negative result for urine β -HCG (test must have a sensitivity of at least 25 mIU/mL) must be available prior to each administration of IP. If the β -HCG test is positive, indicating that the subject is pregnant prior to completing the specified dose regimen, then no further IP

INO-4800	COVID19-311
Inovio Pharmaceuticals, Inc.	Clinical Protocol

will be administered. Every attempt should be made to follow pregnant subjects for the remainder of the study and to determine the outcome of the pregnancy (see Section 7.12).

DIARY

Diaries will be implemented in the Phase 2 segment of the protocol and at selected sites (estimated to include 711 subjects) in the Phase 3 segment. Subjects will be provided a diary to record the following solicited local and systemic AEs:

- Oral temperature and time taken (each daily entry before 11:59 pm)
- Solicited systemic symptoms
- Solicited local injection site symptoms
- Concomitant medications

The diary should be completed once daily starting the evening of each study dose through 6 days post-dose. The completed diary post-dose 1 and post-dose 2 will be reviewed with the subject by the study staff during the next study phone call or visit and collected at the next in-person study visit. The study staff will review the diary with the subject to assess for temperature, solicited systemic symptoms (unusually tired/feeling unwell, muscle aches, headache, nausea, joint pain) and solicited injection site symptoms (pain, itching, redness, swelling, bruising). In addition, unsolicited symptoms and concomitant medications will be assessed.

Any diary entry determined to meet the Common Terminology Criteria for Adverse Events version 5.0 (CTCAE) criteria for a Grade 1 or higher adverse event should be documented as an adverse event unless deemed part of the subject's ongoing medical history. Injection site reactions should be graded per the Toxicity Grading Scale for Healthy Adult and Adolescent Volunteers Enrolled in Preventive Vaccine Clinical Trials, issued September 2007 (See Section 6.4.5). If the diary entry does not meet the criteria of a Grade 1 or higher AE as per the relevant guidelines, Investigator clinical judgment can be used to determine whether the entry should be recorded as an AE and documented accordingly in the site's source. For cases where the diary entry and final AE reporting (i.e. grading) do not agree, the reasoning should be recorded in the source documents.

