- d. Dipstick for glucose, protein, and hematuria. Microscopic examination should be performed if dipstick is abnormal.
- e. Serum pregnancy test at Screening. Urine pregnancy test at other visits.
- f. Intradermal injection(s) in skin preferably over deltoid muscle, or alternately over anterolateral quadriceps muscle, followed by EP at Day 0 and Day 28.
- g. Following administration of INO-4800 or placebo, EP data will be downloaded from the CELLECTRA® 2000 device and provided to Inovio.
- h. AEs to be collected from time of consent to Day 56; SAEs, MAAEs, and AESIs to be collected from time of consent to EOS.
- i. On Day 0, cellular sampling requires 64 mL of whole blood (8 Cell Preparation Tubes (CPT), each 8 mL of whole blood) prior to 1st dose. At all other time points, collect 32 mL of whole blood (4 CPT tubes, each 8 mL of whole blood).
- j. On Day 0, humoral sampling requires a total of 17 mL of whole blood (two 10-mL red top serum collection tubes, each 8.5 mL of whole blood, to produce eight serum aliquots of 1 mL each). At all other time points, collect 8.5 mL of whole blood in a single 10-mL red top serum collection tube to produce four serum aliquots of 1 mL each.
- k. SARS-CoV-2 antibody.
- I. Saliva specimen at Screening; Nasal swabs and saliva specimens at COVID-19 assessment and convalescent visits. Genotyping may also be performed on sample(s) collected at the COVID-19 assessment visit.
- m. Subjects will be evaluated during a "COVID-19 assessment visit" when acute COVID-19 is suspected. The assessment visit may be performed in the clinic, in the subject's vehicle or at the subject's home and should be completed within 3 days of symptom onset or within 3 days of a positive result of a SARS-CoV-2 test.
- n. For subjects with confirmed SARS-CoV-2 infection during the trial, a convalescent visit should be scheduled approximately 28 days after symptom onset, or in the absence of symptoms, the date of positive SARS-CoV-2 test. If acute symptoms are ongoing, the site should follow up with the subject via phone call or an unscheduled visit after symptom resolution or stabilization.
- o. Diary should be reviewed at the 7-day post-dose phone call and collected at the next in-office visit.
- p. Vital signs to be performed at COVID-19 assessment and convalescent visits include temperature, respiration rate, heart rate and oxygen saturation.

CONFIDENTIAL

INO-4800 Inovio Pharmaceuticals, Inc.

TABLE 4 – PHASE 3 SEGMENT SCHEDULE OF EVENTS

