	Sc	D	0	Tel #1		Vk 4	Wk 6	Tel #2-6	Wk 18	Tel #7-11	Wk 30	Tel #12-13	Wk 42	Tel #14-16	Wk 56	Illness	Illness
Day 0	u day u	4 (±3d)	Day 28	(±3d))k	3, 70, 84,)	()	140, 154 ±5d)	()	238, 266	()	8 (±5d)	d)	ent visit ⁱ	ent visit ^m		
Tests and assessments	Screen ^a	Pre	Post	Phone call - Day 14	Pre	Post	Day 42 (±5d) ^k	Phone call - Days 56, 7 98, 112 (±5d)	Day 126 (±5d)	Phone calls - Days 140, 168, 182, 196 (±5d)	Day 210 (±5d)	Phone calls - Days 238, (±5d)	Day 294 (±5d)	Phone calls Days 322, 350, 378 (±5d)	Day 393 (± 5d)	COVID-19 assessment visit ^I	COVID-19 convalescent visit ^m
Informed Consent	Х																
Inclusion/Exclusion Criteria	Х																
Medical history	Х	Х															
Demographics	Х																
Socio-behavioral Assessment	Х																
Concomitant Medications	Х	Х		Х	Х		Х	Х	Х	Х	Х	Х	Х	Х	Х	Х	Х
Physical Exam ^b	Х	Х			Х		Х		Х		Х		Х		Х	Х	Х
Vital Signs	Х	Х			Х		Х		Х		Х		Х		Х	Xn	Xn
Height and Weight	Х																
HIV Serology		Х															
Pregnancy Test ^c	Х	Х			Х												
INO-4800 or Placebo + EP ^d		Х			Х												
Download EP Data ^e			Х			Х											
Adverse Events ^f	Х	Х	Х	Х	Х	Х	Х	Х	Х	Х	Х	Х	Х	Х	Х	Х	Х
Cellular Samples ^g		Х					Х				Х				Х	Xr	Х
Humoral Samples ^h		Х					Х				Х				Х	Xr	Х
SARS-CoV-2 Serology ⁱ	Х	Х			Х		Х		Х		Х		Х		Х		Х
SARS-CoV-2 RT-PCR		х														X٥	
(Nasopharyngeal swabs)		^														^	
Distribute Diary ^p			Х			Х											
Review/Collect Diary ^q				X	Х		Х										

a. Screening assessment occurs from -30 days to -1 day of Day 0. Screening and Day 0 visits may be combined if eligibility is able to be confirmed prior to dosing. If so, all assessments for Screening and Day 0 must be performed at the combined visit.

b. Full physical examination only at Screening and Day 393 (or EOS). Targeted physical exam at other indicated visits.

INO-4800 Inovio Pharmaceuticals, Inc.

- c. In women of childbearing potential. Urine pregnancy test at all indicated visits.
- d. Intradermal injection(s) in skin preferably over deltoid region, or alternately over anterolateral quadriceps region, followed by EP at Day 0 and Day 28.
- e. Following administration of INO-4800 or placebo, EP data will be downloaded from the CELLECTRA® 2000 device and provided to Inovio.
- f. AEs to be collected from time of consent to Day 56; SAEs, MAAEs, and AESIs to be collected from time of consent to EOS.

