6.1.1 CLINICAL TRIAL SCREENING EVALUATIONS

The assessments performed during Screening will determine the subject's eligibility for the study and also their ability to comply with protocol requirements by completing all screening assessments. The following screening evaluations will be performed for both Phase 2 and Phase 3 segments within 30 days prior to dosing on Day 0. All screening assessment values must be reviewed prior to the first Study IP administration. Screening and Day 0 visits may be on the same day if eligibility is able to be confirmed prior to randomization. If so, all assessments for Screening and Day 0 must be performed at the combined visit.

If a subject does not meet an inclusion or exclusion criterion due to a transient and nonclinically significant event at Screening, relevant Screening evaluations may be repeated within the same 30-day Screening period. If the subject fails twice, they will be considered a screen failure.

- Signed and dated informed consent (Section 6.2);
- Review and confirm all inclusion/exclusion criteria (Section 4.1 and 4.2);
- Obtain and document complete medical history, surgical history (including all clinically significant procedures within the past 12 weeks), present conditions and concomitant illnesses (Section 6.1.1.1);
- Collect demographics;
- Collect socio-behavioral assessment information (Section 6.4);

- Collect AEs (Section 6.4.4);
- Record current concomitant medications/treatments (Section 6.4.6);
- Full physical examination (Section 6.4);
- Record vital signs (Section 6.4);
- Record height and weight (Section 6.4);
- Collect urine for pregnancy test (Section 6.4);
- Collect serum for SARS-CoV-2 antibody testing (Section 6.4.8).

Phase 2 segment only:

- Collect blood for CBC with differential and serum chemistry (Section 6.4);
- Collect urine for routine urinalysis (Section 6.4);
- Collect saliva for SARS-CoV-2 RT-PCR (Section 6.4.8).

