6.1.2.1 Day 0 and Day 28 (Dosing Visits)

The following evaluations will be performed on **Day 0 and Day 28 prior to dose administration**:

INO-4800	COVID19-311
Inovio Pharmaceuticals, Inc.	Clinical Protocol

Both Phase 2 and Phase 3 segments:

- Collect all present and/or new or ongoing AEs (Section 6.4.4);
- Document any present conditions and concomitant illnesses;
- Record current concomitant medications/treatments (Section 6.4.6);
- Obtain any updates to medical history, surgical history (including all clinically significant procedures within the past 12 weeks), present conditions and concomitant illnesses (Day 0 visit only) (Section 6.1.1.1);
- Targeted physical examination (Section 6.4);
- Record vital signs (Section 6.4);
- Collect urine for urine pregnancy test (Section 6.4);
- Collect blood for HIV serology (Day 0 visit only) (Section 6.4);
- Collect whole blood and serum for cellular and humoral immunology assessment (Day 0 visit only) (Phase 3 cellular immunology collection at selected sites only) (Section 6.5);
- Review restrictions for injection and EP (Section 6.4.7);
- Randomize subject (instructions to be provided under separate cover) (Day 0 visit only).

Phase 2 segment only:

- Collect blood for CBC with differential and serum chemistry (Section 6.4);
- Collect urine for routine urinalysis (Section 6.4);
- Collect diary from Day 0 dose (Day 28 visit only).

Phase 3 segment only:

- Collect serum for SARS-CoV-2 antibody testing (Section 6.4.8);
- Collect nasopharyngeal swabs for SARS-CoV-2 RT-PCR (Day 0 only) (Section 6.4.8);
- Collect diary from Day 0 dose during Day 28 visit only(for selected sites only).

The following evaluations will be performed on **Day 0 and Day 28 after IP plus EP administration**:

- Collect any new AEs (Section 6.4.4);
- Download EP Data;
- Provide supplies for subject to use at home, as required (e.g. thermometer, wound guide);
- Phase 2 segment: Distribute diary;
- Phase 3 segment, for selected sites: Distribute diary.

6.1.2.2 **Post-dose phone calls**

Phase 2 segment: Day 7 and Day 35

Phase 3 segment: Day 14

The following evaluations will be performed at this visit:

- Collect all present and/or new or ongoing AEs (Section 6.4.4);
- Document any present conditions and concomitant illnesses;
- Record current concomitant medications/treatments (Section 6.4.6);

Phase 2 segment only:

• Review diary (Section 6.4).

Phase 3 segment only:

• Review diary (for selected sites)(Section 6.4);

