6.1.2.6 Day 393 Visit or EOS

Phase 2 and Phase 3 segments: The following evaluations will be performed at this visit:

- Collect all present and/or new or ongoing AEs (Section 6.4.4); SAEs, AESIs, and MAAEs will be reported after the Day 56 Visit;
- Document any present conditions and concomitant illnesses;
- Record current concomitant medications/treatments (Section 6.4.6);
- Ask about any symptoms of COVID-19 disease;
- Full physical examination (Section 6.4);
- Record vital signs (Section 6.4);

Phase 2 segment:

- Collect blood for CBC with differential and serum chemistry (Section 6.4);
- Collect urine for routine urinalysis (Section 6.4);
- Collect whole blood and serum for cellular and humoral immunology assessment (Section 6.4.6);
- Collect urine pregnancy test (Section 6.4).

Phase 3 segment:

- Collect serum for SARS-CoV-2 antibody testing (Section 6.4.8);
- Collect whole blood and serum for cellular and humoral immunology assessment (Phase 3 cellular immunology collection at selected sites only) (Section 6.5).

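### Section 6.4 of Versions 1.0USA and 2.0USA lets a partner's sterility remove a fertile woman from mandated pregnancy testing before dosing

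*Protocol*

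**What the plan says.** The Pregnancy Testing paragraphs of Section 6.4 have the same wording on this point in Versions 1.0USA and 2.0USA. They open with the limit "Pregnancy testing will be performed on women of childbearing potential (WOCBP"). Every woman is then presumed to be WOCBP unless she falls under one of two exceptions. The first is post-menopausal status. The second is "Women who are surgically sterile or have a partner who is sterile", explained by vasectomy in males or by tubal ligation or absent ovaries or uterus in females, with a six-month wait after a vasectomy.

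The Phase 2 and Phase 3 testing instructions that follow are each addressed to WOCBP. Table 4 (Phase 3), footnote c, repeats the limit: "In women of childbearing potential. Urine pregnancy test at all indicated visits".

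Some other lines do not restate it:
- Section 6.4 says that a negative urine beta-HCG "must be available prior to each administration of IP".
- The visit lists say "Collect urine for pregnancy test (Section 6.4") at Screening, "Collect urine for urine pregnancy test (Section 6.4") at the dosing visits, and "Collect urine pregnancy test (Section 6.4") at Day 393 in Phase 2.
- Table 3 (Phase 2), footnote e, reads "Serum pregnancy test at Screening. Urine pregnancy test at other visits".

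On eligibility, Section 4.1.2 criterion f offers three routes: post-menopausal (f.1), own or partner's sterility (f.2), or effective contraception (f.3).

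**The concern.** The two WOCBP exceptions repeat eligibility routes f.1 and f.2 almost word for word, but the two lists answer different questions. Criterion f asks whether pregnancy is adequately prevented. The WOCBP definition decides who is checked for being pregnant. A partner's sterility bears on the first question in the way a contraceptive method does, and it does not alter the woman's own fertility.

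The consequence is uneven. Women relying on a method under f.3 are tested, while a woman relying on her partner's vasectomy is not. Two safeguards depend on a test result: exclusion criterion d in Section 4.2.2 (positive urine test at screening or just before dosing) and the Section 6.4 rule that no further product is given after a positive beta-HCG. Without a test, an unrecognised early pregnancy in such a woman would not be picked up before either dose.

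**Working it through.** There is no statistical figure to reproduce. The check is a comparison of text for one concrete participant: a pre-menopausal woman, not surgically sterile, whose partner had a vasectomy more than six months ago.

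1. **Eligibility.** She meets Section 4.1.2 f.2 through her partner, so f.3 contraception is not asked of her.

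2. **WOCBP status.** Section 6.4 presumes she is WOCBP, then removes her through the partner half of the second exception. She is not WOCBP.

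3. **Tests addressed to WOCBP.** The pregnancy-test row of Table 4 marks Screening, Day 0 and Day 28: 1 + 1 + 1 = 3 tests per WOCBP in Phase 3. By footnote c and the Phase 3 instruction in Section 6.4, the number mandated for her is 0.

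4. **A comparable woman on f.3.** She is fertile and uses an intrauterine device. Neither exception applies, so she is WOCBP and all 3 tests are mandated. The two women differ only in how pregnancy is prevented.

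5. **Whether other text brings her back in.**
 - The beta-HCG sentence stands under a heading whose first sentence confines testing to WOCBP.
 - Each visit-list line refers the reader to Section 6.4 and so takes on its limit.
 - Table 3 footnote e only assigns serum or urine to visits.
 - Read literally, the visit lists would also require tests of men and post-menopausal women, which cannot be intended.

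 None of these lines mandates a test for her on its natural reading.

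6. **Safeguards that do not need a test.** These are inclusion b (non-pregnant), exclusion c (pregnant, breastfeeding or intending pregnancy), the six-month wait, the Section 6.4.7 instruction to avoid pregnancy until the last dose, the medical-history update at Day 0, and the Section 7.12 rule to stop product once staff learn of a pregnancy. All depend on someone already knowing or suspecting.

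7. **Effect of the correction.** With the partner wording removed from the exceptions she becomes WOCBP. The tests mandated in Phase 3 go from 0 to at most 3. Screening and Day 0 may be combined, so three separate occasions are not assured. These counts describe workload and do not measure risk.

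**The case against.** The strongest defence is that this is a coherent choice. The WOCBP exceptions mirror f.1 and f.2, so WOCBP are the women who must use contraception under f.3. That also makes the note in Section 1.4.2.2 true, where the protocol says its inclusion criterion requires effective contraception in women of childbearing potential. The harm is remote: her partner counts as sterile only six months after vasectomy, she must be non-pregnant and not intend pregnancy, and fetal effects are listed among events not observed with these products. Phase 3 requires contraception only until the last dose, so conception soon afterwards is already accepted.

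Most of this stands, and it limits the size of the point. It does not explain why one way of preventing pregnancy should cancel a test that the other ways do not. The remark about Section 1.4.2.2 is also right: deleting the clause alone would leave that note untrue for her, so the fix has to cover it.

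A reader might infer something stronger, that the protocol contradicts itself by exempting this woman in one place and requiring her test in others. The documents do not support that. The unqualified lines either refer back to Section 6.4, sit under its WOCBP limit, or only state the sample type. They are best read as deferring to the definition.

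**Conclusion.** The point holds as a cheap improvement to participant safety that should be made. Under Section 6.4 of Versions 1.0USA and 2.0USA, a fertile woman admitted through her partner's sterility has no mandated pregnancy test at Screening or before either dose, and two test-based safeguards cannot operate for her.

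The gain is small. The documents do not allow the number of such women to be derived, and few missed pregnancies are likely. No endpoint, sample size or analysis is touched. Section 1.3.7 describes Phase 2 dosing as already given, so the benefit is limited to Phase 3 dosing under the USA versions.

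The conclusion rests on reading the unqualified lines as deferring to the Section 6.4 limit. It does not extend to Version 7.0, whose Section 6.4 is not shown, and the pages available do not say which version governs the remaining Phase 3 dosing. Nor do they support a claim that harmful fetal exposure is to be expected.

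**What to change.** In the WOCBP exceptions of Section 6.4, delete the partner clause (the second half of the quoted exception), the mention of vasectomy in males, and the six-month vasectomy sentence. Testing then depends only on the woman's own status. Keep partner sterility, with its six-month wait, as a route in the reproductive-capacity inclusion criterion (Section 4.1.1 g and Section 4.1.2 f.2).

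Reword the note on fetal effects in Section 1.4.2.2 to say that women of childbearing potential must meet that inclusion criterion, through effective contraception or a sterile partner.

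The cost is three short deletions and one reworded note, plus at most three urine tests per affected Phase 3 woman at visits already in the schedule.
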